9.3. Analysis Sets

For purposes of analysis, the following analysis sets are defined:

Population	Description
Safety Analysis Set	All participants randomly assigned to study intervention and who receive at least 1 dose of study intervention. Participants will be analyzed according to the product they actually received.

Defined Population for Analysis	Description
Modified Intention to Treat (mITT)	All participants randomly assigned to study intervention and who apply at least 1 dose of study intervention.
PK concentration set	All enrolled participants who applied at least one dose of PF-07242813 and in whom at least once concentration value is reported.

9.4. Statistical Analyses

The SAP will be developed and finalized before any analyses are performed and will describe the analyses and procedures for accounting for missing, unused, and spurious data. This section is a summary of the planned statistical analyses of the primary and secondary endpoints.

9.4.1. Efficacy Analyses (Part 2 Only)

Endpoint	Statistical Analysis Methods
Secondary (percent change from baseline)	A landmark analysis using analysis of covariance of percent change from baseline in EASI, adjusting for the baseline EASI score, to estimate the effect of the initially randomized treatment in the absence of prohibited medication. The analysis will use the mITT analysis set. Missing data due to any cause including censoring due to initiation of prohibited medication will be imputed using the corresponding vehicle arm, missing data in a vehicle arm will be imputed using data from the vehicle arm assuming data are missing at random (MAR). The analysis will combine the results from the multiple imputations using Rubin's rule's as implemented in SAS PROC MIANALYZE.
CCI	[REDACTED]
[REDACTED]	[REDACTED]

[REDACTED]

[REDACTED]

[REDACTED]

9.4.2. Safety Analyses

Endpoint	Statistical Analysis Methods
Primary	
The safety data will be summarized in accordance with Pfizer Data Standards. All participants who receive study intervention (safety population) will be included in the safety analyses. All safety data will be summarized descriptively through appropriate data tabulations, descriptive statistics, categorical summaries, and graphical presentations. Safety endpoints for the study include:
 
• Treatment-emergent AEs and SAEs;• Withdrawals from active treatment due to AEs;• Serious infections, defined as any infection (viral, bacterial, and fungal) requiring hospitalization or parenteral antimicrobials;• Safety laboratory tests (eg, hematology [including coagulation panel], chemistry and lipid profiles);• ECG and cardiac telemetry changes from baseline;• Vital signs. 
Change from baseline on laboratory data and vital signs will be additionally summarized. Participant listings will also be produced for these safety endpoints.
 
CC1

9.4.2.1. Electrocardiogram Analyses

Changes from baseline for the ECG parameters QT interval, heart rate, QTc interval, PR interval, and QRS complex will be summarized by treatment and time.

The number (%) of participants with maximum postdose QTc values and maximum increases from baseline in the following categories will be tabulated by treatment:

Safety QTc Assessment

Degree of Prolongation	Mild (msec)	Moderate (msec)	Severe (msec)
Absolute value	>450-480	>480-500	>500
Increase from baseline		30-60	>60

In addition, the number of participants with uncorrected QT values >500 msec will be summarized.

If more than 1 ECG is collected at a nominal time after dose administration (for example, triplicate ECGs), the mean of the replicate measurements will be used to represent a single observation at that time point. If any of the 3 individual ECG tracings has a QTc value >500 msec, but the mean of the triplicates is not >500 msec, the data from the participant's individual tracing will be described in a safety section of the CSR in order to place the >500-msec value in appropriate clinical context. However, values from individual tracings within triplicate measurements that are >500 msec will not be included in the categorical analysis unless the average from the triplicate measurements is also >500 msec. Changes from baseline will be defined as the change between the postdose QTc value and the average of the time-matched baseline triplicate values on Day -1, or the average of the predose triplicate values on Day 1.

CCI

9.4.3. Pharmacokinetics Analyses

9.4.3.1. Analysis Population

The PK concentration population is defined as all randomized participants who received a dose of PF-07242813 and in whom at least 1 serum concentration value is reported. The PK parameter analysis population is defined as all randomized participants who received a dose of PF-07242813 and who have at least 1 of the PK parameters of interest calculated.

9.4.3.2. Derivation of Pharmacokinetic Parameters

9.4.3.2.1. Pharmacokinetic Parameters for Part 1

The PK parameters to be assessed, their definition, and method of determination are listed in [Table 6](#). Actual PK sampling times will be used in the derivation of PK parameters.

Table 6. Serum PK Parameters for Part 1

Parameter	Definition	Method of Determination
Single Dose		
AUC _{last}	Concentration-time profile from time zero to the time of the last quantifiable concentration (C _{last})	Linear/Log trapezoidal method
AUC _{last(dn)}	Dose normalized AUC _{last}	AUC _{last} /Dose
AUC _{inf} ^a	Area under the serum concentration time- profile from time zero extrapolated to infinite time	AUC _{last} + (C _{last} [*] /k _{el}), where C _{last} [*] is the predicted serum concentration at the last quantifiable time point estimated from the log-linear regression analysis
CCI		
C _{max}	Maximum serum concentration	Observed directly from data
C _{max(dn)}	Dose normalized C _{max}	C _{max} /Dose
T _{max}	Time for C _{max}	Observed directly from data as time of first occurrence
t _{1/2} ^a	Terminal elimination half-life	Log _e (2)/k _{el} , where k _{el} is the terminal phase rate constant calculated by a linear regression of the loglinear -concentration time- curve. Only those data points judged to describe the terminal log-linear decline will be used in the regression
CCI		
Multiple Doses		
AUC _τ	Area under the serum concentration time- profile over the dosing interval τ where $\tau=2$ weeks/336 hours	Linear/Log trapezoidal method
CCI		
C _{max}	Maximum serum concentration	Observed directly from data
CCI		

Parameter	Definition	Method of Determination
$t_{1/2a}$	Terminal elimination half-life	$\log_e(2)/k_{el}$, where k_{el} is the terminal phase rate constant calculated by a linear regression of the loglinear -concentration time- curve. Only those data points judged to describe the terminal log-linear decline will be used in the regression
CL/F and CL ^a	Apparent clearance for SC dosing (CL/F) and Systemic clearance (CL) for IV dosing	Dose/AUC _t , if steady state is achieved
Vz/Fa	Apparent volume of distribution following SC dosing	Dose/AUC _{inf} * k_{el}
F	Apparent bioavailability of SC injection	AUC _t (SC, sd)/AUC _{14 days} (IV, sd)

^a If data permit.

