Healthy participants who are enrolled into the multiple dose cohorts will be randomized to receive PF-07242813 or placebo every 2 weeks (Q2W) for a total of 3 doses. Participants will be confined to the clinical research unit starting on the day prior to dosing and through at least 96 hours after the first dose of study intervention and 48 hours after the second and third doses. Participants may remain in house longer at the discretion of the PI due to operational logistics. Participants will return for outpatient visits per the ([Table 2](#)), at least through Day 99 visit (or at least 4 half-lives of PF-07242813 based on observed data). Based on emerging PK data, additional samples may be added to ensure PK is adequately characterized. Based on emerging data from previous and ongoing single and multiple dose cohorts, doses planned may be modified and other doses and/or dosing regimens (eg, Q4W) may be explored. If the exposures in the subsequent dose is projected to exceed the exposure limits pre-specified, after repeat doses, that dose will not be explored.

In addition, a cohort of healthy Japanese adults (Cohort 15, n=5) will be enrolled to receive a single IV administration of PF-07242813 or placebo (4 on PF-07242813 and 1 on placebo). This cohort will be initiated after single dose escalation in healthy participants (SAD) is complete and will enroll in parallel to Part 2.

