4.3. Justification for Dose

4.3.1. Prediction of Human PK and Efficacious dose

Based on the serum PK parameter values observed for PF-07242813 in nonclinical species, the predicted 2-compartment PK parameter values in humans are expected to be the same as those of a typical therapeutic IgG mAb. These values have been reported previously (Dirks and Meibohm 2010; Betts et al. 2018)^{8,2} and were used for the PF-07242813 human PK predictions as follows: 3.2 L for central volume, 2.2 L for peripheral volume, 0.25 L/day for central CL, 0.45 L/day for distributive clearance, 0.26 1/day for SC absorption rate constant and 60% for SC bioavailability. The predicted volume and clearance values resulted in a 17-day $t_{1/2}$ and a 5.4 L V_{ss} .

As there are no validated mechanism-based biomarkers or preclinical disease/efficacy model for human AD, the efficacious dose of PF-07242813 has been projected empirically, as a dose that will achieve >95% CD1a receptor occupancy at steady state trough concentrations at the site of action (skin). A site of action model was used to link PF-07242813 exposure to CD1a receptor occupancy using the PF-07242813 K_D and the predicted human PK parameters, CD1a concentrations in skin and CD1a internalization/turnover rate. Using this approach, the predicted efficacious human dose of PF-07242813 is estimated to be 30 mg SC q4wk. The projected steady state AUC_{tau} ($\tau=4$ weeks/672 hrs), C_{ave} and C_{max} associated with the predicted efficacious dose are 1730 $\mu\text{g.h/mL}$, 2.58 $\mu\text{g/mL}$ and 3.67 $\mu\text{g/mL}$.

4.3.2. Dose Rationale for Part 1

The nonclinical safety profile of PF-07242813 has been adequately characterized to support development into human clinical studies of up to 3 months in duration. No test article-related effects or target organs were identified following once weekly administration of PF-07242813 in a pivotal 13-week cynomolgus monkey toxicity study with the NOAEL defined as the highest dose tested, 200 mg/kg/week (IV). In this study, the C_{max} and AUC_{168H} exposure limit for dose escalation are set to be 1020 μ g/mL and 106000 μ g/mL, respectively, determined as 1/10th of the mean exposures observed at NOAEL in the monkey toxicity study.

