3.1.3. Other Endpoint(s): Tertiary/Exploratory

- *PF-07242813 PK parameters, as data permit: AUC_{last}, dose normalized (dn), AUC_{inf}(dn), C_{max}(dn), CL and V_z/F/V_{ss} after single doses; AUC_{inf}(dn), C_{max} (dn) after each repeated dose; CL/F, CL, V_z/F, accumulation ratio, peak to trough ratio (PTR) after the last repeated dose. F for SC administration.*
- *Incidence of the development of ADA and, if appropriate, NAb against PF-07242813 following single and multiple doses.*
- *Change from baseline in select anterior pituitary hormones levels and hormones regulated by them in blood that may include (but may not be limited to): HGH, IGF-1, TSH, T4 and Cortisol.*
- *Change from baseline in blood cytokine levels that may include, but not be limited to, TNF α , IL-6 and IFN γ if performed in concordance with clinical symptoms of cytokine release.*

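### Protocol Table 6 computes the multiple-dose Vz/F from one dose over an AUC that still contains drug from earlier doses, giving about half the true value; CL/F is correctly conditioned on steady state but will probably not be reportable

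*Protocol*

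**What the plan says.** Protocol 9.4.3.2.1, Table 6, Multiple Doses block, has two relevant rows:

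- Vz/F, described as "Apparent volume of distribution following SC dosing": Dose/AUCinf * kel. As printed, without parentheses, this is not a volume; it is read here as Dose/(AUCinf x kel).
- CL/F (SC) and CL (IV): Dose/AUCtau, "if steady state is achieved".

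Both rows carry the footnote "If data permit". The only AUCinf definition visible is in the Single Dose block: "profile from time zero extrapolated to infinite time".

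SAP 3.1.3 lists CL/F, CL and Vz/F among the tertiary/exploratory PK parameters, in a group that ends with "peak to trough ratio (PTR) after the last repeated dose". Protocol 4.1.1 gives study drug "every 2 weeks (Q2W) for a total of 3 doses". On half-life, Protocol 4.3.1 says "The predicted volume and clearance values resulted in a 17-day" value. The corresponding formula rows of SAP Table 2 are redacted, so whether the SAP repeats or changes these formulas cannot be seen.

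**The concern.** Dose/(AUCinf x kel) is a single-dose formula. It holds only when the AUC in the denominator comes from exactly the dose in the numerator. With a dosing interval shorter than one half-life, a large part of doses 1 and 2 is still in the body when dose 3 is given. An AUC extrapolated to infinity from dose 3 includes that residual drug, so Vz/F comes out too small. The footnote does not prevent this: the data will permit the calculation, and the result will still be wrong.

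At stake is a listed MAD parameter for which the SC cohorts are the only source, since all four planned SC cohorts are multiple-dose. A reported value near 5 L could also pass unnoticed, because it sits close to the 5.4 L Vss that Protocol 4.3.1 predicts.

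A separate, practical question is whether three doses can satisfy the steady-state condition attached to CL/F.

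**Working it through.** **Inputs.** Protocol 4.3.1 gives "3.2 L for central volume, 2.2 L for peripheral volume, 0.25 L/day for central CL, 0.45 L/day for distributive clearance", with SC absorption rate 0.26/day and SC bioavailability 60%. Doses fall on days 0, 14 and 28. The model is linear with two compartments, and the three doses are superposed.

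**Reproducing the protocol's figures (Table 5 and the text of 4.3.2, after dose 3).**

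| | Stated | Recomputed |
|---|---|---|
| 15 mg SC Cmax (µg/mL) | 2.405 | 2.405 |
| 15 mg SC AUC168H (µg·h/mL) | 369.4 | 373.3 |
| 15 mg SC Cave (µg/mL) | 2.092 | 2.100 |
| 15 mg SC 672 h AUC (µg·h/mL) | 1144 | 1132 |
| 1000 mg IV Cmax (µg/mL) | 441.6 | 441.3 |
| 1000 mg IV AUC168H (µg·h/mL) | 50640 | 50204 |
| 1000 mg IV Cave (µg/mL) | 245 | 241.8 |

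All agree within 1.3%. The terminal rate constant is 0.0419/day, a half-life of 16.5 days.

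**True values under this model.**
- CL/F = 0.25/0.6 = 0.417 L/day.
- Vz/F = 0.417/0.0419 = 9.94 L.
- AUCinf of a single 15 mg SC dose = 0.6 x 15/0.25 x 24 = 864 µg·h/mL. Under linear PK this is also the steady-state AUCtau.

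**Vz/F by the printed formula, 15 mg SC.**
- AUCs for the first two dosing intervals are 349 and 579. AUC from dose 3 to infinity is 1663. The total from the first dose is 349 + 579 + 1663, about 2592 (all µg·h/mL, before rounding).
- AUCinf from dose 3: 15/[(1663/24) x 0.0419] = 5.17 L, ratio 5.17/9.94 = 0.52.
- AUCinf from the first dose across all doses: 15/[(2592/24) x 0.0419] = 3.31 L, ratio 0.33.
- AUCinf extrapolated from the first interval alone is unbiased in principle. But only 349/864 = 40% of that AUC is observed before dose 2, and this reading conflicts with reporting after the last dose.

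The ratios are the same at 50, 150 and 300 mg because the model is linear.

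**Check without simulating the profile.** Protocol 4.3.2 states 1144 µg·h/mL over the four weeks after dose 3 at 15 mg. One dose gives only 864 to infinity, so the AUC after dose 3 cannot belong to one dose.

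**Sensitivity to half-life (one-compartment approximation).** The ratio is 1/(1 + r + r²), with r = 2^(-14/half-life). It is 0.57 at 14 days, 0.53 at 17 days and 0.49 at 21 days.

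**CL/F and CL.**
- SC: AUCtau after dose 3 is 706, and 706/864 = 82% of steady state. If the condition were waived, 15/(706/24) = 0.510 L/day against 0.417, or +22%.
- From the protocol's own Cave: 2.092 x 336 = 703, giving 0.512 L/day (+23%).
- IV 1000 mg: AUCtau is 81230 against 1000/0.25 x 24 = 96000, or 85%. If waived, CL is 0.295 L/day against 0.25 (+18%).
- The model reaches 90% of SC steady state at dose 4, 94% at dose 5 and 97% at dose 6.

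**The case against.** The strongest objection concerns CL/F. A reader might infer that its formula also ignores carry-over. It does not: Dose/AUCtau is the correct steady-state expression, and the printed condition exists precisely because drug accumulates. The +22% and +18% errors arise only if the condition is disregarded. If it is respected, CL/F is simply not reported, as the plan provides. This objection stands. What remains is that the planned regimen is unlikely to meet the condition, and that no criterion for judging steady state is given.

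A second objection is that the size of the Vz/F error depends on where AUCinf starts, which the visible text does not fix, and that the SAP formula rows are redacted. This stands in part: the ratio is 0.52 or 0.33 depending on the reading. The only unbiased reading, extrapolation from dose 1 alone, contradicts the SAP's timing.

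Third, a reader might infer that the error affects dose escalation or later SC regimen choice. The documents do not support that. Escalation rests on Cmax and AUC168H (Protocol 4.1.1 and 6.6.1), the secondary repeated-dose endpoints (AUCtau, Cmax, Tmax and half-life) are unaffected, and PK summaries are descriptive (9.4.3.3). The single-dose IV cohorts also supply clearance and volume free of carry-over, and concentrations are listed, so a corrected value could be computed later.

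**Conclusion.** The Vz/F row of Table 6 is wrong for use after the third dose. Under the protocol's predicted parameters it returns about 5.2 L against 9.9 L (ratio 0.52), or 3.3 L (ratio 0.33) if AUCinf is taken from the first dose. The CL/F (CL) row is not a formula error, but with about 82% (SC) or 85% (IV) of steady-state AUCtau after three doses, it will probably yield nothing reportable.

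The figures assume linear PK, the predicted parameters and the planned two-weekly regimen. Protocol 2.2.1.3 reports non-linear, target-mediated PK in monkeys, and 4.1.1 allows other regimens such as Q4W; either would change the ratios. Importance is limited because these are tertiary/exploratory, descriptive parameters.

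**What to change.** In Table 6, Multiple Doses block, and in the corresponding SAP Table 2 rows if they use the same formulas:

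- Derive Vz/F as total dose actually received/(AUC from first dose to infinity x kel), with kel from the terminal phase after the last dose and the denominator in parentheses. Check: 45/[(2592/24) x 0.0419] = 9.94 L, the true model value.
- As an improvement rather than a correction, derive CL/F (or CL) as total dose received/AUC from first dose to infinity when steady state is not achieved. Check: 45/(2592/24) = 0.417 L/day.

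Using the dose received, rather than three times the nominal dose, covers participants who miss a dose.

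The cost is a wording change to two rows. Samples already scheduled to Day 99 suffice: about 5.5% of the AUC after dose 3 lies beyond that day, which is 0.055 x 1663/2592, or about 3.5% of the total. The method still assumes roughly linear PK and needs evaluable sampling across all dosing intervals, so participants with gaps would need a stated rule.

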2.2.1.3. Nonclinical PK

[figure not shown]
Non-linear PK was observed after a single IV dose in cynomolgus monkeys, consistent with TMDD. In the pivotal repeat-dose GLP study, there were no apparent sex-related differences in systemic exposure (as assessed by C_{max} and AUC), and systemic exposure increased with increasing dose and was higher after repeat dosing. **CCI**

The PK of PF-07242813 in humans are expected to be the same as those of a typical therapeutic IgG mAb. Based on a site of action PK/PD model, the predicted efficacious dose of PF-07242813 in humans is 30 mg SC Q4W. The predicted steady-state human AUC_{tau} for the efficacious dose level is 1730 $\mu\text{g}\cdot\text{h}/\text{mL}$ and the predicted C_{max} and C_{av} values are 3.67 and 2.58 $\mu\text{g}/\text{mL}$, respectively.

CCI

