4.1.1. Part 1: Single and Multiple Ascending Dose in Healthy Participants

Part 1 is within-cohort randomized, participant- and investigator- blind, sponsor-open, and placebo-controlled investigation of the safety, tolerability, PK, and immunogenicity following SAD and MAD of PF-07242813.

Approximately 97 healthy adult participants will be enrolled at a single study site into the proposed cohorts listed below. Participants may only participate in one cohort.

Participants in the single dose cohorts will be randomized sequentially as follows:

- Cohort 1 (n=4): 0.3 mg active (n=2) or placebo (n=2), IV;
- Cohort 2 (n=4): 1 mg active (n=2) or placebo (n=2), IV;
- Cohort 3 (n=4): 3 mg active (n=2) or placebo (n=2), IV;
- Cohort 4 (n=8): 10 mg active (n=6) or placebo (n=2), IV;
- Cohort 5 (n=8): 30 mg active (n=6) or placebo (n=2), IV;
- Cohort 6 (n=8): 100 mg active (n=6) or placebo (n=2), IV;
- Cohort 7 (n=8): 300 mg active (n=6) or placebo (n=2), IV;
- Cohort 8 (n=8): 1000 mg active (n=6), or placebo (n=2), IV.

Participants in the multiple dose cohorts, will be randomized as follows:

- Cohort 10 (n=8): 15 mg active (n=6) or placebo (n=2), SC x 3 doses Q2W;
- Cohort 11 (n=8): 50 mg active (n=6) or placebo (n=2), SC x 3 doses Q2W;
- Cohort 12 (n=8): 150 mg active (n=6) or placebo (n=2), SC x 3 doses Q2W;
- Cohort 13 (n=8): 300 mg active (n=6) or placebo (n=2), SC x 3 doses Q2W;
- Cohort 14 (n=8, optional): ≤ 1000 mg IV active (n=6) or placebo (n=2), SC x 3 doses Q2W.

The Japanese Participant Cohort will be randomized as follows:

- Cohort 15 (n=5): a single IV dose active (n=4) or placebo (n=1).

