The dose range of 15 mg to 300 mg SC administered every two weeks (Q2W) in total of 3 doses were selected for dose escalation in 4 MAD cohorts (Table 5). The dosing regimen of every two weeks (Q2W) was selected to achieve high exposures of PF-07242813 with fewer doses compared to monthly dosing for adequate safety assessment. The multiple dose period is planned to be initiated at the 15 mg SC dose level with the C_{max} and AUC_{168H} following 3 repeated doses, each dose predicted to be 424- and 287-fold below the exposure limits pre-defined. The predicted exposures following 3 repeated doses at 15 mg SC are also below the steady-state exposures at projected efficacious dose (30 mg SC Q4W) for both C_{max} (2.405 vs 3.67 μ g/mL) and AUC_{tau} (1144 vs 1730 μ g.h/mL over 4 weeks/672 hrs). At the highest dose proposed (1000 mg IV) in an optional MAD cohort, the predicted margins for C_{max} and AUC_{168H} , relative to the exposure limits, are 2.3- and 2.1-fold, respectively (Table 5).

Table 5. Projected Exposures, Maximum CD1a RO and Safety Margins After the 3rd Dose of Multiple SC or IV Doses of PF-07242813^a

DOSE (mg q2wk) ^b	C_{max} (μ g/mL)	T_{max} (hr)	AUC_{168H} (μ g·hr/mL)	C_{ave}^c (μ g/mL)	SM_ C_{max}^d (fold)	SM_ AUC^d (fold)	SM_ C_{ave}^d (fold)	Max RO ^e (%)
15	2.405	96	369.4	2.092	424	287	302	96.3
50	8.017	96	1231	6.973	127	86	91	98.7
150	24.05	96	3694	20.92	42	29	30	99.6
300	48.1	96	7388	41.84	21	14	15	99.8
1000 IV	441.6	1	50640	245	2.3	2.1	2.6	99.9

- a. Human PK was predicted using 2-CM model with S.C. in which $V_c=3.2$ L, $V_p=2.2$ L, $CL=0.25$ L/day, $Q=0.45$ L/day, 0.26 1/day for SC absorption rate constant and 60% for bioavailability were used. PK parameters after the 3rd dose are presented.
- b. Dose is given q2wk with 3 doses in total. All the doses are given as subcutaneously except 1000 mg which is given IV over 1 hr infusion.
- c. $C_{ave}=AUC_{tau}/336$ ($\tau=336$ hours for q2wk dosing in MAD cohorts).
- d. SM=safety margin, which is calculated relative the exposure limits of $C_{max}=1020$ μ g/mL and $AUC_{168H}=106000$ μ g.h/mL, determined as 1/10th of the mean exposure at NOAEL of 200 mg/kg/week IV in pivotal 13-week cynomolgus monkey toxicity study. C_{ave} used for safety margin calculation is exposure limit of AUC_{168H} divided by 168 hr.
- e. A site of action model was used to predict CD1a receptor occupancy at skin with the predicted human PK.

4.3.3. Dose Rationale for Part 2

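### Protocol Table 6 defines SC bioavailability F with no dose term and no named IV comparator, and its 14-day window is expected to understate F even at equal dose (minor)

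*Protocol*

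**What the plan says.** Protocol Table 6 gives F ("Apparent bioavailability of SC injection") in the multiple-dose block, with the method "AUC _t (SC, sd)/AUC _{14 days} (IV, sd"). The same table sets tau at 336 hours, so both AUCs cover 14 days. The abbreviation list defines SD as single dose and, separately, dn as dose normalized, so the label sd in this row is not a dose term. Other rows of the table do write Dose explicitly, for example for dose-normalised AUClast, dose-normalised Cmax and clearance.

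Protocol 4.1.1 plans SC levels of 15, 50, 150 and 300 mg and single IV levels of 0.3, 1, 3, 10, 30, 100, 300 and 1000 mg. The only dose in both lists is 300 mg: "Cohort 13 (n=8): 300 mg active (n=6) or placebo (n=2), SC x 3 doses Q2W" and "Cohort 7 (n=8): 300 mg active (n=6) or placebo (n=2), IV". The same section says that "doses planned may be modified and other doses and/or dosing regimens" may be explored.

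Protocol 9.4.3.3.1 and SAP 6.1.2 plot dose-normalised AUC by dose and route. SAP 3.1.3 lists F as a tertiary/exploratory parameter. No formula for F is visible in the SAP, and rows of its PK parameter table (Table 2) are redacted.

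**The concern.** There are two separate problems.

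1. **Dose and comparator.** A ratio of raw AUCs equals bioavailability only when the two doses are equal. At any other pairing the printed ratio is off by the factor SC dose/IV dose, and the row leaves the IV cohort open. Two analysts could follow the row and report different values.
2. **Window.** Fourteen days is shorter than the predicted half-life. SC drug enters the circulation later than IV drug, so a 14-day window captures a smaller share of the total SC exposure than of the total IV exposure. Dividing one by the other then gives less than F, even at equal dose.

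What is at stake is limited. F is descriptive, sets no dose in this trial and feeds no test. The risk is that a value labelled bioavailability is carried forward without its comparator or the direction of its bias being known.

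**Working it through.** **Inputs** (Protocol 4.3.1; Tables 4 and 5): linear two-compartment model with Vc 3.2 L, Vp 2.2 L, CL 0.25 L/day and Q 0.45 L/day; "0.26 1/day for SC absorption rate constant and 60% for SC bioavailability"; IV infusion over 1 hour.

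**Reproducing the plan's figures.**

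| Quantity | Protocol | Recomputed |
|---|---|---|
| Cmax, 1000 mg single IV (Table 4) | 311.1 µg/mL | 311.1 |
| AUC168H, 1000 mg single IV (Table 4) | 31650 µg·h/mL | 31272 (1.2% lower) |
| Average concentration, third 15 mg SC dose (Table 5) | 2.092 µg/mL | 2.10 |

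The model is therefore the protocol's own, to within about 1%.

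**Share of exposure inside 14 days, per mg of dose.**
- IV: total AUC = 24/0.25 = 96.0 µg·h/mL; AUC over 14 days = 48.21; share = 48.21/96.0 = 0.502.
- SC: total AUC = 0.60 × 96.0 = 57.6; AUC over 14 days = 23.30; share = 23.30/57.6 = 0.404.
- Dose-normalised ratio = 23.30/48.21 = 0.483, or equivalently 0.60 × 0.404/0.502 = 0.483. Since 0.483/0.60 = 0.81, the ratio is 19% low.

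**The row as printed** = 0.483 × SC dose/IV dose:

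| SC/IV dose (mg) | Printed ratio |
|---|---|
| 15/10 | 0.72 |
| 50/30 | 0.81 |
| 150/100 | 0.72 |
| 300/300 | 0.48 |
| 15/30, 50/100, 150/300 | 0.24 |
| 300/100 | 1.45 |
| 300/1000 | 0.14 |

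The first four rows use the planned IV dose nearest to each SC level. The others use the adjacent IV doses and show how far the answer depends on an unnamed choice.

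**Direction of the window bias.** Under linear PK with first-order absorption, the SC partial AUC is F times an average of IV partial AUCs over shorter windows. The dose-normalised ratio is therefore below F for any finite absorption rate, and it rises with the window: 0.483 at 14 days, 0.556 at 28, 0.579 at 42 and 0.594 at 70.

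**Sensitivity** (F = 0.60, 14 days; the ranges are assumptions, not from the documents):
- Absorption rate 0.15 to 1.0/day: 0.40 to 0.57.
- CL halved or doubled: 0.47 or 0.51.
- Both together: 0.38 (rate 0.15, CL halved) to 0.58 (rate 1.0, CL doubled), that is 36% to 3% low.

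**From Table 5 alone.** Its note says "PK parameters after the 3rd dose are presented". The dose-normalised ratio of average concentrations is (41.84/300)/(245/1000) = 0.57, against the 0.60 used to build the table. This is a third-dose figure, so it does not check 0.483. It does show the same direction in the protocol's own projections.

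**The case against.** The strongest case is that the row may be meant only for the 300 mg pair (Cohort 13 against Cohort 7), where no dose term is needed. Dose-normalised AUC is also a planned parameter in the SAP, so normalisation may be understood, and no text directs anyone to divide raw AUCs at unequal doses. The operative SAP formula may sit in redacted rows, since the SAP may modify the protocol (Protocol 9). The protocol row itself has come through imperfect text extraction. The parameter is called apparent, and 14 days is the longest first-dose SC window available because the second dose falls on Day 15.

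Part of this stands. The equal-dose reading is possible, a dose term may simply have been left out, the 14-day window has a good reason, and the SAP may already differ. The unequal-dose values show what the omission allows; they do not predict what the sponsor will report.

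It does not remove the point. The row is not limited to one pair, doses may change, and neither the plots nor the dose-normalised parameters amend it. The equal-dose pair still gives 0.48 for a true 0.60, and the word apparent does not tell a reader that the AUCs are truncated or in which direction that pushes the result.

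**Conclusion.** The point holds, at minor grade, for the protocol row. As printed, F is not reproducible without choices that the row does not state. With those choices made, it is expected to be about a fifth too low (0.48 against 0.60) under the protocol's predicted PK, or 3% to 36% low over the assumed ranges.

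This rests on linear PK and first-order absorption. The protocol notes: "Non-linear PK was observed after a single IV dose in cynomolgus monkeys, consistent with TMDD". If clearance depends on dose in humans, comparing unequal doses could bias F in either direction even after normalisation, which is a further reason to fix the comparator. Nothing is concluded about the redacted SAP rows.

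**What to change.** In Table 6, write F as [AUCtau(SC, first dose)/SC dose] / [AUC14days(IV)/IV dose]. Fix the IV comparator before F is computed, for example the IV cohort closest in dose to each SC level; as planned, that is Cohorts 4, 5, 6 and 7 for Cohorts 10, 11, 12 and 13. In a footnote, label the result a 14-day partial-AUC ratio that is expected to understate F. Confirm that the SAP row agrees.

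The cost is one table row and a footnote, with no new samples. Cohorts 4 to 7 are outside the shortened follow-up that applies to Cohorts 1 to 3.

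Optionally, where data permit, add a sensitivity estimate from total exposure: [SC AUC over the three doses to infinity/(3 × SC dose)] / [IV AUCinf/IV dose]. This is a trade-off. It removes the window bias but assumes linear, time-invariant PK, and the protocol rates immunogenicity risk as moderate. At predicted CL the extrapolated share is 3.5% for SC followed to Day 99 and 4.8% for IV if the last sample is on Day 71. If CL is halved these become 16.8% and 20.3%; if it is doubled, 0.3% and 0.4%. The extrapolated share should be reported, and the last IV sampling day confirmed against the schedule of activities.
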